### *4.1. Inclusion Criteria*

- 4.1.1 Adults aged 18 to 75 years old
- 4.1.2 Meet the criteria for *1.3 chronic migraine* based on ICHD3 criteria
- 4.1.3 Currently receiving onabotulinumtoxinA per PREEMPT protocol for the treatment of chronic migraine
- 4.1.4 Patient is willing and able to comply with the protocol to the satisfaction of the investigator
- 4.1.5 Patient has the capacity to provide written, informed consent for themselves

[figure not shown]
### *4.2. Exclusion Criteria*

- 4.2.1 Participants with an active implanted electrical and/or neurostimulator device (e.g., cardiac pacemaker, cochlear implant).
- 4.2.2 Participants with congestive heart failure (CHF), severe cardiac or cerebrovascular disease.
- 4.2.3 Participants with uncontrolled epilepsy.
- 4.2.4 Pregnant, trying to get pregnant or breastfeeding female participants
- 4.2.5 Subjects participating in any other interventional clinical study.
- 4.2.6 Participants with other significant pain, medical or psychological problems that in the opinion of the investigator may confound the study assessments
- 4.2.7 Participants who have previous experience with the device
- 4.2.8 Patients with cranial deformities, prior cranial surgeries with violation of the calvarium, or shunt placement
- 4.2.9 Patients receiving concurrent nerve blocks or trigger point injections within the same visit

## **5. Methods:**

CONFIDENTIAL: This document is the intellectual property of [name]. Acceptance of this document constitutes the agreement by the recipient that no unpublished information contained herein will be published or disclosed without prior written approval.

**5.1. Study design:** Single-center, randomized, single-blind, sham-controlled crossover trial

**5.2. Pretreatment phase**

Informed consent in English will be obtained prior to enrollment into the study.

**5.3. Treatment Phase**

Upon receipt of informed consent, the patient will enter phase 1 of the study. This phase is used to determine baseline experience with the PREEMPT protocol and will involve obtaining pre-, intra-, and post-procedural pain intensity levels based on a standard visual analog scale. Subjects will then be contacted the following day to inquire about the presence of post-procedural headache. Following their initial treatment of BoNT-A, subjects will then be randomized to receive either remote electrical neuromodulation with Nerivio® or stimulation with a sham device for their next BoNT-A treatment and enter phase 2. During phase 2, patients will again receive BoNT-A treatment via PREEMPT protocol at week 12 +/- 7 days (buffer period to accommodate rescheduling) and will also be treated with either Nerivio® or receive stimulation with a sham device supplied by **Theranica Bio-electronics, Ltd.** Patients will have the device applied 20 minutes prior to starting the Botox procedure with an estimated total time of wearing the device around 40 to 45 minutes. Again, patients will be surveyed regarding their pre-, intra-, and post-procedural pain intensity and will be contacted on the following day re: post-procedural headache. Finally, patients will receive their final treatment of BoNT-A at week 24 +/- 7 days and will receive concurrent treatment with the alternative stimulation setting (either Nerivio® treatment stimulation or sham stimulation). Pre-, intra-, and post-procedural pain levels and post-procedural headache will be recorded in an identical fashion.

CONFIDENTIAL: This document is the intellectual property of [name]. Acceptance of this document constitutes the agreement by the recipient that no unpublished information contained herein will be published or disclosed without prior written approval.

#### *5.4. Conclusion of study*

The study ends 24 weeks after consent was obtained (excluding potential buffer time to accommodate rescheduling).

### **6. Data Collection and Monitoring**

#### *6.1. Clinical Assessments*

Patients will have received a focused neurological exam at their prior clinic visit and will be surveyed regarding their pre-procedural, intra-procedural, and post-procedural pain, before, during, and after receipt of onabotulinumtoxinA with PREEMPT protocol. Per routine clinical practice, patients will be monitored for 5 minutes post-procedure to ensure lack of acute adverse effects to the procedure.

#### *6.2. Post-procedural headache*

Subjects will be contacted on the day following each administration of onabotulinumtoxinA to inquire about the presence of post-procedural headache, defined as a headache that lasts for 4 hours or more and is at least moderate in severity or during which abortive medications are used to treat the patient's head pain.

#### *6.3. Patient History*

Patient history will be collected to ensure accurate diagnosis of chronic migraines as well as to document currently prescribed abortive and prophylactic migraine medications. Patient medical history and device history will also be reviewed to ensure no contraindications to device administration.

#### *6.4. Lab Work*

None required

## **7. Outcome Measures**

#### *7.1. Primary Outcome Measure*

The primary outcome is the reduction in pain intensity measured via Visual Analog Scale (VAS) among patients at the baseline or sham treatment compared to treatment with remote electrical neuromodulation using Nervio ®.

#### *7.2. Secondary Outcome Measures*

7.2.1. Subjects will be contacted on the day following each administration of onabotulinumtoxinA to inquire about the presence of post-procedural headache, defined as a headache that lasts for 4 hours or more and is at least moderate in severity or during which abortive medications are used to treat the patient's head pain.

#### *7.2.5. Any adverse events.*

#### *7.3. Statistical Analysis*

Subjects will be randomized to treatment vs sham treatment groups utilizing the REDCap. Study data will be collected and managed using REDCap electronic data capture tools hosted at the Mayo Clinic – Arizona. REDCap (Research Electronic Data Capture) is a secure, web-based

CONFIDENTIAL: This document is the intellectual property of [name]. Acceptance of this document constitutes the agreement by the recipient that no unpublished information contained herein will be published or disclosed without prior written approval.

software platform designed to support data capture for research studies, providing 1) an intuitive interface for validated data capture; 2) audit trails for tracking data manipulation and export procedures; 3) automated export procedures for seamless data downloads to common statistical packages; and 4) procedures for data integration and interoperability with external sources (Harris, 2009; Harris 2019).

### *7.3.1 Sample Size Consideration*

Primary endpoint: Pain level change from pre-treatment/pre-sham, intra-treatment/intra-sham, and post-treatment/post-sham

A two-sided t-test achieves 80% to infer that the mean difference (between treatment and sham) is not 0 when the total sample size of a 2x2 cross-over design is 80 with an equal number in each sequence (n=40/sequence) when the actual effect size is 0.45 (standardized difference, medium effect size) and the significance level is 0.05.

### *7.3.2 Statistical Analysis Plan*

Summary statistics will be used to describe the patient population's demographics and clinical characteristics. Patients' pain level change and post-procedure headache after each treatment/sham as well as patients' any adverse events will be summarized in descriptive statistics.

Linear mixed model will be used to analyze the primary outcome for 2 by 2 cross-over study design. Treatment group will be the primary predictor in the model while sequence and period will be adjusted in the model.

Generalized linear mixed model will be used to analyze the effect of treatment on the secondary endpoint presence of post-procedural headache. Similarly, treatment group will be used as the primary predictor while sequence and period will be adjusted in the model.

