Inclusion and Exclusion Criteria	
Inclusion Criteria
 
 
1. Adults aged 18 to 75 years old
 
2. Meet the criteria for 1.3 chronic migraine based on ICHD3 criteria
 
3. Currently receiving onabotulinumtoxinA per PREEMPT protocol for the treatment of chronic migraine
 
4. Patient is willing and able to comply with the protocol to the satisfaction of the investigator
 
5. Patient has the capacity to provide written, informed consent for themselves
 
 
Exclusion Criteria
 
 
1. Participants with an active implanted electrical and/or neurostimulator device (e.g., cardiac pacemaker, cochlear implant).
 
2. Participants with congestive heart failure (CHF), severe cardiac or cerebrovascular disease.
 
3. Participants with uncontrolled epilepsy.
 
4. Pregnant, trying to get pregnant or breastfeeding female participants
 
5. Subjects participating in any other interventional clinical study.
 
6. Participants with other significant pain, medical or psychological problems that in the opinion of the investigator may confound the study assessments
 
7. Participants who have previous experience with the device
 
8. Patients with cranial deformities, prior cranial surgeries with violation of the calvarium, or shunt placement
 
9. Patients receiving concurrent nerve blocks or trigger point injections within the same visit
 

Measurements	Subjects will be surveyed on their pain intensity using a Visual Analog Scale pre-, intra- and post-procedure (approximately 0 – 5 minutes post-procedure). Additionally, patient demographic information (sex, age, race, ethnicity), BMI, arm circumference, depression/anxiety screen, medical comorbidities, headache qualities (location, duration, intensity, frequency, associated symptoms), previous rounds of onabotulinumtoxinA received, current treatment regimen (beyond onabotulinumtoxinA) including other preventive and abortive treatments will be recorded. Migraine-specific quality measures (MIDAS) will also be recorded throughout the study period. Patients will be contacted on the day following each treatment of onabotulinumtoxinA to follow-up on post-procedural headache.

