Outcomes	
Primary: Pain intensity with a Visual Analog Scale, pre- , intra-, and post-procedure
 
Secondary:
 
 
1. Presence of post-procedural headache
 
2. Any adverse events.
 

CONFIDENTIAL: This document is the intellectual property of [name]. Acceptance of this document constitutes the agreement by the recipient that no unpublished information contained herein will be published or disclosed without prior written approval.

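### Optional, cheap precision gain: the valid primary crossover model does not use the same-visit pre-procedure VAS as a covariate, and the timing of that rating relative to the device is not stated

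*Combined protocol and SAP*

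**What the plan says.** The model in section 7.3.2 has three fixed effects: "Treatment group will be the primary predictor in the model while sequence and period will be adjusted in the model". No section names a baseline covariate.

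The rating itself is planned. The Synopsis (Measurements) states: "Subjects will be surveyed on their pain intensity using a Visual Analog Scale pre-, intra- and post-procedure". Section 5.3 repeats this for phase 2 ("patients will be surveyed regarding their pre-, intra-, and post-procedural pain intensity") and has phase 3 recorded in the same way.

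The role of the pre-procedure rating differs between sections:

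- The Synopsis (Outcomes) counts it among the primary ratings: "Pain intensity with a Visual Analog Scale, pre- , intra-, and post-procedure".
- Section 7.1 speaks of a "reduction in pain intensity measured via Visual Analog Scale (VAS) among patients at the baseline or sham treatment", compared with Nerivio, and does not mention the pre-procedure rating.
- Section 7.3.1 words the endpoint as "Pain level change from pre-treatment/pre-sham, intra-treatment/intra-sham, and post-treatment/post-sham".
- Section 7.3.2 refers to "pain level change and post-procedure headache after each treatment/sham", but in the sentence on descriptive summaries. Its model sentence says only that the primary outcome will be analysed.

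On timing, section 5.3 says: "Patients will have the device applied 20 minutes prior to starting the Botox procedure". Sections 5.3 and 6.1 tie the pre rating to the injection procedure, not to device application. The wording in 7.3.1 suggests a pre-device rating, but no section says so.

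**The concern.** Patients with chronic migraine may arrive with different amounts of head pain at different visits. If that visit-to-visit variation carries into the intra- or post-procedure rating, it is noise in the within-patient comparison, and the pre-procedure VAS can remove some of it. The plan pays for this information and then either leaves it out (raw outcome) or uses it in one fixed way (change score, slope 1). What is at stake is precision, not validity.

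Timing comes in because a covariate must not itself be affected by treatment. The device starts 20 minutes before the injections. A pre-procedure rating taken during those 20 minutes could already carry part of the effect.

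**Working it through.** **Inputs.** From section 7.3.1: N = 80, 40 per sequence, standardised effect 0.45, two-sided alpha 0.05, power 80%. Assumed, because the documents give no values: r, the within-patient correlation between the pre and later ratings; and k, the within-patient SD of the pre rating divided by that of the later rating.

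**1. The plan's own figure.** Reading 0.45 in units of the within-patient SD, the standard error is SD × √(2/80). The noncentrality is 0.45 × √40 = 2.846 on 78 df, which gives power of 80.3%. The stated 80% reproduces.

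**2. Raw VAS outcome.** The covariate multiplies the within-patient error variance by (1 − r²). It costs one within-patient df (77 left). Chance imbalance in the covariate inflates the variance by 1 + 1/76 = 77/76 = 1.013 on average. Noncentrality is therefore 0.45 × √(40 / [(1 − r²) × 77/76]). For r = 0.5 this is 0.45 × √(40 / [0.75 × 1.013]) = 3.265.

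| assumed r | 1 − r² | power |
|---|---|---|
| 0 | 1.00 | 79.7% |
| 0.1 | 0.99 | 80.1% |
| 0.2 | 0.96 | 81.3% |
| 0.3 | 0.91 | 83.3% |
| 0.5 | 0.75 | 89.7% |
| 0.7 | 0.51 | 97.4% |

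The comparator is 80.3%. Break-even is near r = 0.115. The loss at r = 0 is 80.3 − 79.7, about 0.5 point before rounding.

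**3. Change-score outcome.** Relative to the later rating's variance, an unadjusted change score has error variance 1 + k² − 2rk and the covariate model has 1 − r². Their ratio is (1 − r²)/(1 + k² − 2rk).

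| k | r = 0 | 0.2 | 0.3 | 0.5 | 0.7 |
|---|---|---|---|---|---|
| 0.5 | 0.80 | 0.91 | 0.96 | 1.00 | 0.93 |
| 1 | 0.50 | 0.60 | 0.65 | 0.75 | 0.85 |
| 1.5 | 0.31 | 0.36 | 0.39 | 0.43 | 0.44 |

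The ratio never exceeds 1, because the denominator minus the numerator is (k − r)². These ratios leave out the lost df and the 1.013 factor. With both included, and 0.45 taken as the standardised effect on the change score, the covariate model loses about 0.5 point where r is close to k. At k = 0.5 it is slightly worse for r from about 0.40 to 0.59. Steps 2 and 3 have different comparators and should not be set against each other.

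**4. Form of the covariate.** Splitting the rating into patient mean and visit deviation makes the treatment estimate use only the within-patient slope. With complete pairs it equals a paired-difference ANCOVA to machine precision. It also gives the same treatment estimate and standard error whether the outcome is raw VAS or change at a given time point.

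A single unsplit term in a random-intercept model mixes the two slopes. In a simulation (4,000 trials per cell, N = 80, REML, equal between- and within-patient SDs, k = 1, Monte Carlo error about 0.6 point) with between-patient correlation 0.8 and within-patient r = 0, power was 80.2% unadjusted, 75.5% with the single term and 79.5% split. At within-patient r = 0.5 the single and split forms were close (88.6 and 89.1%). With between-patient correlation 0.5 and r = 0, the single term gave 78.5% against 80.0% unadjusted.

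**5. Timing.** Suppose an on-device pre rating already carries a fraction f of the effect, with k = 1. A change score then keeps 1 − f of the effect and a covariate-adjusted estimate about 1 − rf. For illustration, f = 0.3 and r = 0.5 give 0.70 and 1 − 0.15 = 0.85.

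**The case against.** The strongest reply is that nothing is broken. The model is a standard crossover analysis, every figure for the gain rests on an assumed correlation, and the gain may be nil or slightly negative. If the change wording in 7.3.1 governs, the pre rating is already used, and the gap is only between a fixed and an estimated slope. All of this stands, and it is why the point is optional.

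Three stronger readings are tempting but are not supported:

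- *That leaving out the covariate biases the result or leaves the trial short of its stated power.* Sequence is randomised and period is in the model, so the contrast does not need the covariate to be valid, and the stated power reproduces without it.
- *That the split is the only acceptable form.* A paired-difference ANCOVA gives the same estimate. A single raw term loses clearly only when the between-patient slope is strong and the within-patient slope is weak. It is less safe, not wrong in every case.
- *That an on-device rating may never be the subtracted baseline.* Change from a pre-device rating can include relief of headache already present. Change from an on-device rating taken just before injection is closer to the pain added by the injections. Which is wanted is a choice of estimand that the documents do not settle.

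Nor do the documents show that the rating is taken with the device on; they leave the order open.

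**Conclusion.** This is an optional improvement, not an error. For a raw outcome, adding the covariate moves power from 80.3% to between 79.7 and 97.4% over assumed within-patient correlations of 0 to 0.7. Against a change score, the error-variance ratio runs from about 0.31 to 1.0 for k between 0.5 and 1.5. The worst case is about half a power point, when r is near 0 (raw outcome) or near k (change outcome). The calculations assume 0.45 is in within-patient SDs, one outcome value per visit, complete pairs and a pre-device rating. Where in the range this trial falls cannot be derived from the documents. The timing gap stands even if the covariate is declined, because a change score depends on it too.

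**What to change.** 1. For the procedural VAS outcome that the sponsor confirms as primary, add the same-visit pre-procedure VAS to the model in 7.3.2. Either split it into patient mean and visit deviation, or use the equivalent paired-difference ANCOVA.
2. Use it as a covariate only if, in phases 2 and 3, it is rated before the device is applied, and state that timing in 5.3 and 6.1.
3. Say that this rating is the baseline and not one of the primary outcomes listed in the Synopsis.
4. If a change score is kept, state whether the subtracted rating is pre-device or on-device. Phase 1 has no device, so also state which phase 1 rating corresponds to it for any comparison with baseline under 7.1.
5. Settle this before the interim analysis at 50% completion (7.3.3), so that the covariate is not chosen after data have been seen.

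Cost: two model terms, of which one uses a within-patient df (78 to 77), a sentence on timing and a sentence on the rating's role. No new data are needed. The statistical downside is the half point given above.

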### *7.3.3 Interim Analysis Plan*

Interim analyses: One interim analysis will be conducted after 50% of patients have completed the 24 weeks study period. The interim analysis will include the below stopping rule for efficacy and futility based on Lan-DeMets spending function with O'Brien-Fleming boundaries. Occurrence of adverse events will also be evaluated at the interim analysis.

Accrual	Total Number	Efficacy boundary (Z scale)	Alpha spent	Futility boundary (Z scale)	Beta spent
50%	40	+/- 2.96	0.003	+/- 0.35	0.04
100%	80	+/- 1.95	0.05	+/- 1.95	0.2

CONFIDENTIAL: This document is the intellectual property of [name]. Acceptance of this document constitutes the agreement by the recipient that no unpublished information contained herein will be published or disclosed without prior written approval.

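### Does the final bound of 1.95 in the interim analysis table let the type I error exceed 0.05?

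*Combined protocol and SAP*

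**What the plan says.** Section 7.3.3 (Interim Analysis Plan) schedules a single look: "One interim analysis will be conducted after 50% of patients have completed the 24 weeks study period". It continues: "The interim analysis will include the below stopping rule for efficacy and futility based on Lan-DeMets spending function with O'Brien-Fleming boundaries". The table then gives:

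- at 40 patients, an efficacy bound of ±2.96 (alpha spent 0.003) and a futility bound of ±0.35 (beta spent 0.04);
- at 80 patients, ±1.95 for both efficacy and futility (alpha 0.05, beta 0.2).

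Both boundary columns are labelled as being on the Z scale.

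Section 7.3.1 (Sample Size Consideration) sets the design: "A two-sided t-test achieves 80% to infer that the mean difference (between treatment and sham) is not 0", with 40 patients in each sequence, and "the significance level is 0.05". Section 7.3.2 (Statistical Analysis Plan) names the analysis: "Linear mixed model will be used to analyze the primary outcome for 2 by 2 cross-over study design", adjusted for sequence and period.

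No section says whether the futility stop is binding or non-binding. None says how the mixed model's test statistic is to be set against the Z-scale bounds.

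**The concern.** A final critical value of 1.95 has a nominal two-sided p-value of 0.0512. After one interim look for efficacy, a reader expects a final bound above 1.96. A lower one is legitimate only if the futility stop removes some null trials that would otherwise have gone on to reject. That requires that no efficacy claim ever follows an interim |Z| below 0.35, and the plan does not say so. Under the null such a crossing occurs in 27% of trials. Because the look comes after 40 patients have finished 24 weeks, others may be part-way through the crossover, and their data could tempt someone to test again.

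The second worry is scale. The bounds are Z values, while the sample size uses a t-test and the analysis a mixed model. If raw t statistics with 38 and 78 degrees of freedom were compared with 2.96 and 1.95, the test would be too liberal. At stake in both cases is whether the primary comparison keeps its two-sided level of 0.05.

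**Working it through.** **Inputs.** Two-sided alpha 0.05, power 80%, effect size 0.45 and 80 patients (section 7.3.1); one look at information fraction 40/80 = 0.5, and the printed bounds (section 7.3.3).

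**Sample size.** With the effect size read against the within-patient SD, the drift is 0.45 × √(80/2) = 2.846. Normal-approximation power is Φ(2.846 − 1.960) = 81.2%, and 80.3% by the t distribution with 78 df. The stated 80% is reproduced.

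**Spending at the interim.** O'Brien-Fleming-type spending in each tail:

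- alpha: 4[1 − Φ(z(0.0125)/√0.5)] = 4[1 − Φ(2.241/0.707)] = 0.00305, which gives |Z| = 2.963. The table prints 0.003 and 2.96.
- beta: 4[1 − Φ(z(0.05)/√0.5)] = 4[1 − Φ(1.645/0.707)] = 0.0400. The table prints 0.04.

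**Futility and final bounds.** Z1 and Z2 have correlation √0.5. The futility bound b, final bound c and drift are solved together for 80% power, by numerical integration.

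- Binding: P(|Z1| ≥ 2.963) + P(b ≤ |Z1| < 2.963, |Z2| ≥ c) = 0.05 under the null. Solution: drift 2.827, b = 0.3490, c = 1.9526, which print as 0.35 and 1.95.
- Non-binding: the same equation with the |Z1| < b region kept. Solution: drift 2.843, b = 0.3557, c = 1.9686, which would print as 0.36 and 1.97.

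Both printed values match the binding solution and neither matches the non-binding one.

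**Type I error with the printed bounds, Z scale.**

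- Futility obeyed: 0.0503. The 0.0003 excess comes from printing 1.9526 as 1.95.
- Every crossing overridden and run to 80: add P(|Z1| < 0.35, |Z2| > 1.95) = 0.00187, so 0.05029 + 0.00187 = 0.0522. The crossing itself has null probability 0.2737.
- Only already-enrolled patients completed and then tested at 1.95: the documents give no accrual duration. With uniform accrual over A weeks, the number enrolled at the look is min(80, 40 + 1920/A), that is 80 for A of 48 or less, 67 for A = 72 and 60 for A = 96. The type I error is then 0.0522, 0.0511 and 0.0506.

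**Type I error on t statistics** (simulated null crossover trials with 38 and 78 df, one outcome per period, complete data):

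- Bounds applied as nominal two-sided p-values (2.96 = 0.0031, 0.35 = 0.726, 1.95 = 0.0512): 0.0506 with futility obeyed.
- Raw t compared directly with 2.96 and 1.95: 0.0550 obeyed, 0.0569 overridden.

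**What non-binding bounds would buy.** With 2.96, 0.36 and 1.97, the Z-scale type I error is 0.0481 obeyed and 0.0499 overridden. Power at drift 2.846 with futility obeyed falls from 80.6% to 80.0% on the Z scale, and from 79.7% to 79.1% with nominal p-values on t statistics. At the final analysis, the two sets of bounds decide differently only for p between 0.0488 and 0.0512.

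**The case for a change.** The best case for a change is that a final bound looser than 1.96 should not rest on an unwritten condition. Investigators do sometimes continue past a futility bound. Section 10 leaves monitoring to the investigating physicians, and no section says what becomes of patients in mid-study at the look. Bounds of 0.36 and 1.97, applied as p-values, would keep the error at or below 0.05 whichever way the trial went, for three table cells and a few sentences. The scale point is also genuine: a literal comparison of t with the table exceeds 0.05 even when futility is obeyed.

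The arithmetic behind this stands, and so does the observation that two details are unstated. The inference that the plan needs changing does not. A rule that stops for futility is, on its ordinary meaning, obeyed, and the plan describes no efficacy test after a crossing. A final bound below 1.96 is normal for such a design. The Z-scale label already tells the analyst to convert the model's p-value to a normal quantile; silence about that step is not evidence that raw t will be used. Choosing between binding and non-binding futility is a design decision, and the non-binding version exchanges a little power for a freedom that the plan does not ask for. It would also bring power on t statistics to 79.1%, slightly further below the stated 80%.

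**Conclusion.** The boundary table is correct to rounding, and no change is needed. Followed as written, the type I error is 0.0503 on the Z scale and about 0.0506 with p-values converted to normal quantiles, against a nominal 0.05. The 0.0522 is a ceiling that requires every futility crossing to be overridden and the trial completed to 80. The 0.0550 requires raw t statistics to be set against bounds labelled as Z values. Neither is planned.

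What remains is a gap that analysts fill sensibly (futility obeyed, bounds read as nominal p-values) and a fair trade-off over non-binding futility, worth about 0.5 points of power.

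This rests on an information fraction of 0.5 at the look, on the within-patient SD reading of the 0.45 effect size for the power figures and, for the t-based figures, on one outcome value per period with complete data. The binding reading is inferred from the wording and from the two printed bounds, since the plan does not state it.
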